5.2.2.2 Adverse event and serious adverse event reporting

The residual effect period (REP) for afatinib is 28 days after last intake of afatinib.

All adverse events, serious and non-serious, occurring from signing of the informed consent/patient assent for trial participation onwards until the FU visit i.e. 28-30 days after last administration of study medication, regardless of relatedness and listedness, will be collected, documented and reported to the sponsor by the investigator.

SAEs and AESIs occurring after the FU visit (28-30 days after last administration of study medication) will be reported in case they are considered relevant by the investigator.

All AEs, including those persisting after end of study medication must be followed up until they have resolved or have been sufficiently characterised, unless the sponsor and the investigator agree not to pursue them further. Reporting will be done according to the specific definitions and instructions detailed in the adverse event reporting section of the ISF. A summary of the AE reporting requirements is given in [Table 5.2.2.2:1](#).

Proprietary confidential information.

© 2017 Boehringer Ingelheim International GmbH or one or more of its affiliated companies. All rights reserved.

This document may not - in full or in part - be passed on, reproduced, published or otherwise used without prior written permission.

Table 5.2.2.2:1 AE/SAE reporting requirements

Time period	Reporting requirements
From signing of informed consent for trial participation* to the FU visit (\leq 28-30 days after last trial drug administration) *Does not apply to pre-screening consent	Report all AEs and SAEs regardless of relatedness or whether the trial drug was administered. This includes all deaths.
Post-treatment: after the FU visit ($>$ 28-30 days after last trial drug administration)	Report only SAEs which are considered relevant by the investigator

The investigator must report the following events via fax using the SAE form immediately (within 24 hours) to the sponsor:

- SAEs
- non-serious AEs which are relevant for the reported SAE/AESI
- protocol-specified AESIs

BI has set up a list of AEs which are defined to be always serious. In order to support the investigator with the identification of these “always serious adverse events”, a query will be raised if a non-serious AE is identified to be serious per BI definition. The investigator must verify the description and seriousness of the event. If the event description is correct, the item “serious” needs to be ticked and an SAE has to be reported in expedited fashion following the same procedure as above.

The list of these adverse events can be found via the RDC-system and in the ISF.

SAEs occurring in patients after having discontinued in the trial due to screening failures. i.e. after the screening period and who did not receive any trial medications, are to be reported if the investigator considered the SAE related to the screening procedure. SAEs which occurred during the screening period are to be reported according to standard procedure.

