5.2.2.1 Definitions of adverse events

Adverse event

An adverse event (AE) is defined as any untoward medical occurrence, including an exacerbation of a pre-existing condition, in a patient in a clinical investigation who received a

Proprietary confidential information.

© 2017 Boehringer Ingelheim International GmbH or one or more of its affiliated companies. All rights reserved.

This document may not - in full or in part - be passed on, reproduced, published or otherwise used without prior written permission.

pharmaceutical product. The event does not necessarily have to have a causal relationship with this treatment.

An AE can therefore be any unfavourable and unintended sign (including an abnormal laboratory finding), symptom, or disease temporally associated with the use of a medicinal product, whether or not considered related to the medicinal product.

Serious adverse event

A serious adverse event (SAE) is defined as any AE which results in death, is immediately life-threatening, results in persistent or significant disability / incapacity, requires or prolongs patient hospitalisation, is a congenital anomaly / birth defect, or is to be deemed serious for any other reason if it is an important medical event when based upon appropriate medical judgement which may jeopardise the patient and may require medical or surgical intervention to prevent one of the other outcomes listed in the above definitions.

Cancers with new histology are always considered serious.

The following hospitalizations are not considered to be serious adverse events (SAEs) because there is no “adverse event” (i.e., there is no untoward medical occurrence) associated with the hospitalization:

- Hospitalizations for respite care
- Planned hospitalizations required by the protocol (including anaesthesia for imaging exams)
- Hospitalization planned prior to informed consent (where the condition requiring the hospitalization has not changed post study drug administration)
- Hospitalization for administration of study drug

Intensity of adverse event

The intensity of the AE should be judged based on the following:

- The intensity of adverse events should be classified and recorded according to the Common Terminology Criteria for Adverse Events (CTCAE) v3.0 in the (e)CRF.

Causal relationship of adverse event

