Medical judgment should be used to determine the relationship, considering all relevant factors, including pattern of reaction, temporal relationship, de-challenge or re-challenge, confounding factors such as concomitant medication, concomitant diseases and relevant history. Assessment of causal relationship should be recorded in the case report forms.

Yes: There is a reasonable causal relationship between the investigational product administered and the AE.

No: There is no reasonable causal relationship between the investigational product administered and the AE.

Proprietary confidential information.

© 2017 Boehringer Ingelheim International GmbH or one or more of its affiliated companies. All rights reserved.

This document may not - in full or in part - be passed on, reproduced, published or otherwise used without prior written permission.

The reason for the decision on causal relationship needs to be provided in the eCRF and on the SAE form (if applicable).

Worsening of the underlying disease or other pre-existing conditions

Worsening of pre-existing conditions other than underlying disease will be recorded as an (S)AE in the (e)CRF.

Exemptions to SAE Reporting

Disease Progression is a study endpoint for analysis of efficacy. Disease progression is exempted from reporting as a (S)AE. Progression of the patient's underlying malignancy, including death due to progression of the underlying malignancy, will be recorded in the appropriate pages of the (e)CRF as part of efficacy data collection.

Examples of exempted events of PD are:

- Progression of underlying malignancy (Progressive disease PD): if PD is clearly consistent with the suspected progression of the underlying malignancy as defined by the respective response criteria.
- Hospitalization/Procedures due solely to the progression of underlying malignancy (PD)
- Clinical symptoms and/or signs of progression (with or without confirmation by objective criteria e.g. imaging, clinical measurement): if the symptom can exclusively be determined to be due to the progression of the underlying malignancy and does meet the expected pattern of progression for the disease under study.

However, when there is evidence suggesting a causal relationship between the drug and the progression of the underlying disease, the event must be reported as (S)AE in the eCRF and on the SAE Form.

Changes in vital signs, ECG, physical examination, and laboratory test results

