7.8.1 Adverse events

The analyses of adverse events (AE) will be descriptive in nature. All analyses of AEs will be based on the number of patients with AEs and not on the number of AEs. For analysis of duration, severity etc. of multiple AE occurrences, data on the case report form (CRF) will be collapsed into AE episodes provided that all of the following applies:

- The same MedDRA lowest level term was reported for the occurrences.
- The occurrences were time-overlapping or time-adjacent (time-adjacency of two occurrences is given if the second occurrence started on the same day or on the day after the end of the first occurrence).
- Treatment did not change between the onset of the occurrences or treatment changed between the onsets of the occurrences, but no deterioration was observed for the later occurrence.

For further details on summarization of AE data, please refer to the BI guideline (4).

The analyses of adverse events will be based on the concept of treatment-emergent adverse events. That means that all adverse events occurring between first drug intake and 28 days after last drug intake or death, whichever occurs first, will be assigned to the on-treatment period. All adverse events occurring before any study drug intake will be assigned to 'screening' and all adverse events occurring after last study drug intake + 28 days will be assigned to 'Off-treatment' (for listings only). For details on the treatment definition, see [Section 6.1](#).

An overall summary of adverse events will be presented. The frequency of patients with adverse events will be summarised by highest CTC grade (grades 1, 2, 3, 4, 5 and all grades), treatment, primary system organ class and preferred term for each of the following AE tables as well as relatedness of AEs to treatment and seriousness:

- DLTs (1st course and all courses)
- All AEs
- Drug-related AEs
- AEs leading to dose reduction
- AEs leading to treatment discontinuation
- Drug-related AEs leading to dose reduction
- Drug-related AEs leading to treatment discontinuation
- AEs leading to death
- Serious AEs
- Drug related serious AEs
- Other significant AEs, defined as AEs leading to dose reduction or permanent discontinuation of study medication
- Non-serious AEs with higher than 5% occurrence rate for disclosure on ClinicalTrials.gov

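### Protocol 5.2.2.1 exempts progression deaths from (S)AE reporting, Table 5.2.2.2:1 asks for all deaths, and the SAP has no rule for progression deaths entered as AEs

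*Protocol*

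**What the plan says.** **Protocol 5.2.2.1, exemptions to SAE reporting.** "Disease progression is exempted from reporting as a (S)AE". Progression of the tumour, "including death due to progression of the underlying malignancy, will be recorded in the appropriate pages of the (e)CRF", that is, with the efficacy data. There is one way back into safety reporting: "when there is evidence suggesting a causal relationship between the drug and the progression of the underlying disease, the event must be reported as (S)AE".

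**Protocol 5.2.2.2, Table 5.2.2.2:1.** For the period from trial consent to the follow-up visit the instruction is: "Report all AEs and SAEs regardless of relatedness or whether the trial drug was administered. This includes all deaths". The only exception attached to that row is "Does not apply to pre-screening consent". The table does not mention progression or refer back to Section 5.2.2.1. The text above it presents the table as a summary and adds: "Reporting will be done according to the specific definitions and instructions detailed in the adverse event reporting section of the ISF". That site file is not among the documents.

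**SAE definition, Protocol 5.2.2.1.** "A serious adverse event (SAE) is defined as any AE which results in death". SAEs go to the sponsor on the SAE form within 24 hours (5.2.2.2).

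**SAP 7.8.1.** Patients with AEs are counted by worst CTC grade, Grade 5 included, with separate tables for "AEs leading to death" and for serious AEs. The on-treatment window runs from first intake to 28 days after last intake, or to death if earlier. The section sends the reader to Protocol 5.2.2.1 for AE definitions. It has no instruction to remove, flag or separately count progression deaths that reached the AE pages.

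**The concern.** Take a child who dies of tumour progression 20 days after the last dose, with no suspicion that the drug contributed. One section says this is not an (S)AE and belongs on the efficacy pages. The other, read at face value, says the death is to be reported. The protocol does not say which governs.

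Such deaths are plausible here. Protocol 1.1 cites survival of 4 to 6 months from relapse in high grade glioma, and 2-year survival from relapse of 3.6% and 2.5% in DIPG. About 30 sites are expected (3.3), so handling could differ between sites. The trial has one arm, so any difference in handling enters the reported rates directly. The DMC also receives AE listings (3.1.1).

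At stake is whether the all-cause fatal-AE, Grade 5 and SAE counts mean the same thing for every patient.

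**Working it through.** The plan states no figure on this point, so there is none to reproduce. The check sets the two texts side by side and follows one death through the SAP outputs.

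**Step 1. One progression death, judged unrelated to the drug, within the on-treatment window**

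| Output | Section 5.2.2.1 followed | Table 5.2.2.2:1 followed |
|---|---|---|
| Fatal AEs, patients | adds 0 | adds 1 |
| AEs by worst grade, Grade 5 | adds 0 | adds 1 |
| Serious AEs, patients | adds 0 | adds 1 only if the patient has no other SAE |
| Drug-related AE and SAE tables | adds 0 | adds 0 |
| DLT and MTD | no change | no change |
| Objective response, PFS | no change | no change |

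The third row follows because SAP 7.8.1 counts patients, not events. DLTs require relatedness to afatinib (Protocol Table 4.1.4.1:2), so the MTD cannot move. PFS counts death from any cause and is not driven by AE reporting.

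**Step 2. Size per death**

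Inputs: N = 38 for the expansion part (Synopsis; Protocol 3.3) and N = 55 for the whole trial (Protocol 7.6), which is 17 + 38.

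Shift in the fatal-AE rate, in percentage points = 100 × m / N, where m is the number of on-treatment progression deaths that were entered as AEs.

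- m = 1, N = 38: 100 × 1/38 = 2.6
- m = 1, N = 55: 100 × 1/55 = 1.8

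38 is the planned number evaluable for response, while SAP 7.8 uses treated patients. If more are treated, each death weighs slightly less.

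**Step 3. Range**

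The documents do not give m. Purely to show the scale, assume m = 4, 8 or 11 of 38:

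- 100 × 4/38 = 10.5
- 100 × 8/38 = 21.1
- 100 × 11/38 = 28.9

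These are illustrations, not forecasts. Under mixed practice m is smaller than the number of progression deaths, because it counts only those entered under the table's wording.

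**The case against.** The best defence is that the two texts can be read together. The exemption is specific: it names death from progression and says where to record it. The table is general and is offered only as a summary. On that reading its deaths are a subset of the reportable AEs and SAEs, and progression has already been taken out of that class. The site file may say so outright. Protocol 8.2 provides training for all investigators and on-site monitoring, and the SAP refers to the very section that holds the exemption.

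Much of this stands. It is a reasonable reading, and the site file may have produced uniform practice.

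It does not remove the inconsistency. The table has its own sentence on deaths, with no qualifier. It lists one exception, so a reader may expect any other to be there too. Section 5.2.2 sends readers to this table for the reporting requirements, and no order of precedence is given. The SAP's reference to 5.2.2.1 supplies definitions but does not say what to do with a progression death already in the AE data.

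A reader might infer that sites in practice work from the table. The documents say nothing of the kind; they direct reporting to the site file.

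**Conclusion.** Wrong as written, of low to moderate severity. The protocol gives two statements on progression deaths that do not agree on their face, and the SAP does not harmonise the result. The all-cause fatal-AE and Grade 5 tables can move by 2.6 points per such death in the expansion part, or 1.8 points in the whole trial. The serious-AE table moves less, since patients with another SAE are already counted.

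This rests on two assumptions: that some patients die of progression within the on-treatment window, and that the site file does not already settle the rule. The affected set is narrow. It covers progression deaths with no suspected drug causality, and the conflicting instruction ends at the follow-up visit, after which only SAEs the investigator considers relevant are reported.

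Two stronger conclusions are tempting and not supported. One is that the fatal-AE rate will swing by tens of points: no document gives a rate of such deaths, and a full swing would compare every site following the table with none doing so. The other is that fatal toxicity is hidden: the drug-related tables leave out deaths judged unrelated, and the dose-finding conclusion is untouched.

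**What to change.** 1. **Protocol.** Reconcile Table 5.2.2.2:1 with Section 5.2.2.1 so that both state the same rule for deaths due solely to progression, with a cross-reference. Keep the exception for suspected drug causality. Check that the site file agrees, and tell sites.
2. **Data.** Query fatal AE records already entered, to identify those due solely to progression.
3. **SAP 7.8.1.** Present fatal AEs and serious AEs with and without deaths due solely to progression. Add a table of causes of death; this is already a safety endpoint in Protocol 5.2.1, but the available text of SAP 7.8 lists no table for it.

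The cost is one table cell, a site letter, a limited set of queries and a few extra outputs. No endpoint, sample size or treatment rule changes. If data collection is already complete, items 2 and 3 carry the repair.

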5.2.2.3 Pregnancy reporting

In very rare cases, pregnancy might occur in paediatric clinical trials. Once a female patient has been enrolled into the clinical trial, after having taken study medication, the investigator must report immediately any drug exposure during pregnancy to the sponsor. Drug exposure during pregnancy has to be reported immediately (within 24 hours) to the defined unique entry point for SAE forms of the respective BI OPU (country-specific contact details will be provided in the Investigator Site File). The outcome of the pregnancy associated with the drug exposure during pregnancy must be followed up. In the absence of an (S)AE, only the Pregnancy Monitoring Form for Clinical Trials and not the SAE form is to be completed. The ISF will contain the Pregnancy Monitoring Form for Clinical Trials (consists of Part A and Part B).

Proprietary confidential information.

© 2017 Boehringer Ingelheim International GmbH or one or more of its affiliated companies. All rights reserved.

This document may not - in full or in part - be passed on, reproduced, published or otherwise used without prior written permission.

5.2.3 Assessment of safety laboratory parameters

Safety laboratory samples will be analyzed at the investigator's local laboratory. Safety laboratory examinations will include hematology, biochemistry and urine examinations. Table 5.2.3: 1 presents the laboratory tests to be performed at screening, Day1 of each course and/or EOT whatever applies.

Table 5.2.3:1 Clinical Laboratory Tests

Category	Parameters
Haematology	Haemoglobin (Hb), platelet count, white blood cell count (WBC), with differential (neutrophils, lymphocytes, monocytes)
Coagulation	International Normalized Ratio (INR), activated Partial Thromboplastin Time (aPTT)
Chemistry	
Electrolytes	sodium, potassium, calcium, magnesium, chloride, bicarbonate (HCO ₃)
Liver function tests	alkaline phosphatase, aspartate aminotransferase (AST), alanine aminotransferase (ALT), γ -glutamyltransferase (GGT), total bilirubin
Renal function parameters	Blood urea/blood urea nitrogen (BUN), creatinine; Creatinine clearance estimate by institutional standard formula for estimation of GFR in paediatric patients.
Category	Parameters
Other	glucose, albumin, phosphorus, lactate dehydrogenase (LDH), total protein, uric acid, creatine phosphokinase (CK); in case of pathological CPK further evaluation (e.g by determination of isoenzymes, troponin assays, ECG exam) should be performed as clinically indicated, CRP
Urinalysis	pH, protein, glucose, erythrocytes, leucocytes, nitrite and, if clinically indicated ketones, urobilinogen, specific gravity; in case of pathological finding(s) further evaluation should be performed and results of the latter must be documented
Pregnancy test	β -HCG testing in urine or serum in girls of childbearing potential (WOCBP)

Proprietary confidential information.

© 2017 Boehringer Ingelheim International GmbH or one or more of its affiliated companies. All rights reserved.

This document may not - in full or in part - be passed on, reproduced, published or otherwise used without prior written permission.

Limited lab tests (Hb, WBC, ANC, thrombocytes) will be required at intermediary visits

The investigator should complete additional evaluations of laboratory tests as clinically indicated. Any abnormal findings from these investigations need to be reported as an Adverse Event. For confirmation of laboratory findings indicative for drug induced liver injury (DILI), local laboratories will be used

5.2.4 Electrocardiogram

12-lead ECG will be taken at the time points specified in the [Flow Chart](#). The investigator will review the ECG recording, comment on any clinical significance and if applicable record any ECG abnormality that meets AE criteria.

5.2.5 Assessment of other safety parameters

5.2.5.1 Physical examination, vital signs, height and weight, performance score

A full physical exam must include: vital sign measurements blood pressure [systolic blood pressure, diastolic blood pressure], pulse rate, temperature, cardiopulmonary examination, examination of the regional lymph nodes, and examination of the abdomen and an assessment of the mental and neurological status. Additional symptoms which have not been reported during a previous examination must be clarified. Wherever possible the same investigator should perform this examination.

A complete physical examination will be done at Screening, Day 1, every visit on study, and at the End-of-Treatment visit.

Measurement of height (in cm), body weight (in kg) and the evaluation of the performance score (Lansky for patients ≤ 12 years or Karnofsky for patients older than 12 years at the time of informed consent) will be conducted at the times specified in the [Flow Chart](#).

5.2.5.2 Left ventricular function

LVEF will be assessed by echocardiography (ECHO) at time points specified in the [Flow Chart](#).

5.2.5.3 Ophthalmologic examination

Standard ophthalmological examination to exclude keratitis will be conducted at time points specified in the [Flow Chart](#).

5.2.5.4 Pulmonary examination

Pulmonary examination must include transdermal O₂ saturation at time points specified in the [Flow Chart](#) and may be supplemented by a chest X-ray if clinically indicated.

5.3 OTHER

5.3.2 Other assessment(s)

5.3.3 Pharmacogenomic evaluation

Not applicable

5.4 APPROPRIATENESS OF MEASUREMENTS

The US NCI CTCAE criteria version 3.0 ([R04-0474](#)) are used in the assessment of adverse events in cancer patients.

Proprietary confidential information.

© 2017 Boehringer Ingelheim International GmbH or one or more of its affiliated companies. All rights reserved.

This document may not - in full or in part - be passed on, reproduced, published or otherwise used without prior written permission.

